# 7. RESEARCH QUESTION AND OBJECTIVES

Information on prescribing of filgotinib for UC under real-world clinical practice is scarce, specifically, in the context of the updated prescribing information and HCP Guide after implementation of Article 20 decisions on JAKi's.

Therefore, this longitudinal DUS aims to describe physicians' adherence to the prescribing information of filgotinib in real-world clinical practice and to evaluate the effectiveness of the aRMMs by assessing how HCPs prescribing filgotinib adhere to the information provided in the SmPC in conjunction with the information in the HCP Guide with a specific focus on aRMMs implemented after the EC Article 20 decision on JAKi's (i.e. after 10 March 2023).

The objectives of this study are as follows:

- a. To describe the characteristics of patients treated with filgotinib in terms of:
- Demographics (e.g., age and sex)
- Comorbidities and prior and current medication use
- b. To evaluate prescribers' adherence to the filgotinib aRMMs, specifically:
- Compliance with the recommended posology (average daily dose) and duration of use
- Compliance with recommendations for patient screening and laboratory monitoring prior to and during treatment
- Compliance to recommendations for use in patients with moderate to severe chronic renal impairment/end stage renal disease or severe hepatic impairment
- Compliance with recommendations for limitations of use, including:
  - Use in patients with risk factors for venous thromboembolism (VTE)
  - Use in patients aged 65 years and older
  - Use in patients with risk factors for cardiovascular (CV) disease
  - Use in patients with risk factors for malignancy

- Use in patients with risk factors for serious infections
- Use in patients with concomitant use of other potent immunosuppressants
- Use of live attenuated vaccines
- Contraindicated use
- Compliance with discontinuation of filgotinib treatment in patients experiencing VTE

## 8. **RESEARCH METHODS**

## 8.1. Study Design

This DUS is based on a non-interventional, post-authorization, prospective, multicountry, registry-based, longitudinal follow-up (cohort) design with secondary use of data collected from 3 European IBD registries. The registries to be used are: (i) the ENEIDA Register from Spain (ES), (ii) the ICC Register from the Netherlands (NL), and (iii) SWIBREG from Sweden (SWE). Data from the 3 European IBD registries may be enriched with additional (secondary) data collection information if needed and applicable. The study fulfills the criteria of a non-interventional PASS (category 3) in accordance with the commitment to the EMA and to the MHRA from the United Kingdom.

The study population will include up to 500 consecutive adult patients of any sex with UC and initiating treatment with filgotinib following implementation of the aRMMs after EC's final decision on Article 20 (decision date: 10 March 2023) per registry.

The observational period will be 4 years starting after the EC decision date on Article 20 (i.e. after 10 March 2023). It will include all follow-up time until dropout for the included patients.

Two reports will be generated: an interim report with 2 years of data collection (to be submitted within 9 months after end of interim data collection), and a final study report with 4 years of data collection (to be submitted within 12 months after end of data collection).

*Note*: The end of data collection, i.e. the timepoint by which the analytical dataset to perform the statistical analyses is completely available, is highly correlated with the process of chart abstraction (ENEIDA) or data linkage (SWIBREG). Thus, interim and final study reports will not be available within 9 and 12 months, respectively from the end of the observational periods.

In addition, in the ENEIDA registry, the set-up of ethics approvals, contracts and necessary activities (e.g. trainings) with all individual centers before chart abstraction can begin will likely take up to 2 years, based on prior experience in conducting similar PASS in this registry. It is important to keep this in mind for the scope of the interim report since it will be limited to information readily available in the ENEIDA registry (i.e. without supplementing its information with chart abstraction).

The chosen design of a prospective non-interventional registry-based follow-up study allows the investigation of the specific research questions of this DUS using the data collection infrastructure of 3 existing and established IBD registries based on real-world data (European Medicines Agency, 2021). In addition, the 3 data sources have been combined into 1 common

protocol to align the data collection process of this study as much as possible aiming for increased consistency in design (Klungel et al., 2016).

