Furthermore, aRMMs are in place to mitigate important identified and potential risks associated with the use of filgotinib. These include a healthcare professional (HCP) Guide designed to increase awareness among HCPs by delivering specific information on contraindications, and warnings and precautions. Moreover, there is a patient alert card (PAC) to enhance awareness of risks and early signs and symptoms relating to specific adverse drug reactions and the best course of action to take.

On 10 February 2022, the Pharmacovigilance Risk Assessment Committee (PRAC) started a review of the safety of JAKi's for treatment of various chronic inflammatory disorders (including UC) under Article 20 of Regulation (EC) No 726/2004 (European Medicines Agency, 2022). This was triggered by the results of the 'Oral Surveillance Study' – an open-label, non-inferiority, post-authorization safety RCT involving patients with active rheumatoid arthritis aged  $\geq$  50 years and with at least one additional cardiovascular (CV) risk factor. The study suggested an increased risk of major adverse cardiovascular events (MACE) and malignancies in patients treated with the JAKi tofacitinib compared with tumor necrosis factor (TNF) $\alpha$  inhibitor treated patients (Ytterberg et al., 2022).

On 10 March 2023, with the EC's final decision on Article 20, the measures recommended by PRAC to minimize the risk of serious adverse events with JAKi's (including CV conditions, VTE, malignancies and serious infections) were endorsed. It was recommended that JAKi's should only be used in patients aged 65 years or above, those at increased risk of MACE, those who smoke or have done so for a long time in the past, and those at increased risk of malignancies "if no suitable treatment alternatives are available".

Based on the above PRAC recommendations and the approved key concepts in the summary of product characteristics (SmPC) (https://www.ema.europa.eu/en/documents/product-information/jyseleca-epar-product-information\_en.pdf), the marketing authorization holder (MAH) of filgotinib updated the existing HCP Guide and the PAC to reflect the changes in SmPC for filgotinib following the EC's final decision on Article 20.

Furthermore, a direct healthcare professional communication (DHPC) was issued to inform prescribers on the identified risks related to serious and opportunistic infections, and the potential risks of malignancies, VTE, and MACE.

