#### 8.2.2. Inclusion Criteria

Across all 3 registries, adult patients ( $\geq$ 18 years) of any sex with UC that are enrolled in 1 of the 3 IBD registries after 10 March 2023 and during the observational period (complying with the register's requirements for inclusion including patient consent) and initiated on filgotinib after 10 March 2023. Initiation is defined as either no prior filgotinib use or prior use that was discontinued before 10 March 2023 (thus, patients who are non-naïve to filgotinib can be included).

There are no restrictions on patient inclusion in terms of either historical data or minimum amount of follow-up.

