## 8.2.4. Index Date, Follow-up

The index date (= start of follow-up) in each registry will be the date a patient starts UC treatment with filgotinib (i.e. the date of first identification of filgotinib exposure in the registry) after the EC decision date. The patient's total follow-up time is defined as the time from the filgotinib index date until the earliest of treatment discontinuation, study withdrawal (withdrawn from the registry, death or loss to follow-up) or end of study.

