Furthermore, not all information that is relevant in the context of this DUS may be captured by all registries. For instance, in the context of skin malignancies (NMSC), none of the registries systemically records information on periodic skin examination. Therefore, this cannot be reliably followed or measured in any of the three registries used in this DUS. Moreover, not all registries capture the same information, nor is the process of data capturing the same. While e.g. in SWIBREG – due to data linkage to various other Swedish data sources and registries – the vast majority of variables will be available, in ENEIDA information on many variables will need to be extracted from EMRs.

The analyses of this DUS will be restricted to the period after the EC decision date on the JAKi Article 20 procedure (10 March 2023), and therefore not include filgotinib data of the pre-referral period. The rationale for this is that the number of patients identified in the registries exposed to filgotinib in the pre-referral period, i.e. between the filgotinib EU approval date (Netherlands: 12-Nov-2021; Spain: 01-May-2023 [= date of reimbursement approval of filgotinib in Spain on a national level]; Sweden: 12-Nov-2021) and the EC decision date is very limited (ICC: n=54; ENEIDA: n=19; SWIBREG n=44).

Any non-interventional study can suffer from bias, specifically, selection or information bias. However, this study aims to capture up to 500 consecutive patients per registry initiating filgotinib in the observational period. Therefore, this study will reflect the clinical practice and characteristics of these patients.

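### Section 8.1 describes starts after the updated risk minimization materials were implemented, but the cohort is selected from the EC decision date, so starts before national distribution are pooled into the evaluation of the updated content

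*Protocol*

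**What the plan says.** Protocol Section 8.1 (Study Design) describes the population as up to 500 consecutive adults with UC per registry, "initiating treatment with filgotinib following implementation of the aRMMs after" the EC decision on Article 20. This makes implementation of the updated materials the starting condition and gives the EC decision date in parentheses.

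The rules that select and follow patients use the decision date alone:

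- Section 8.2.2 (Inclusion Criteria): enrolled in a registry "and initiated on filgotinib after 10 March 2023".
- Section 8.2.3 (Exclusion Criteria): removes only those already on filgotinib, without interruption, at that date.
- Section 8.2.4 (Index Date): "the date of first identification of filgotinib exposure in the registry) after the EC decision date".
- Section 8.1, later in the same section: "The observational period will be 4 years starting after the EC decision date on Article 20".
- Section 8.9 (Limitations): "The analyses of this DUS will be restricted to the period after the EC decision date on the JAKi Article 20 procedure".

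On timing, Section 6 reports that after the EC's final decision the marketing authorization holder "updated the existing HCP Guide and the PAC to reflect the changes in SmPC for filgotinib". It adds, without a date, that a direct healthcare professional communication (DHPC) was issued. Section 7 sets the aim "to evaluate the effectiveness of the aRMMs by assessing how HCPs prescribing filgotinib adhere to the information provided in the SmPC" together with the HCP Guide, with a specific focus on measures implemented after the decision. No section gives the date on which the Guide, card or DHPC reached prescribers in Spain, the Netherlands or Sweden.

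**The concern.** A regulatory decision and the arrival of revised materials in clinics are different events, and the protocol's own account puts the second after the first. A patient who started on 11 March 2023 satisfies Section 8.2.2. That patient satisfies Section 8.1 only if the revised materials were already in place, which the protocol does not say.

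The stated focus is the effectiveness of the updated measures. A decision taken before the updated Guide or DHPC arrived carries no information on whether the update worked. The protocol describes no lag, run-in or calendar split, and Section 8.9 does not list the gap as a limitation.

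Two things are at stake. The reported adherence to updated recommendations mixes decisions made with and without the updated content, and more heavily at the 24-month interim than at 48 months. Also, if distribution dates differ by country, part of any difference between registries could reflect those dates rather than prescriber behaviour.

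**Working it through.** **Dates.** The decision date is 10 March 2023 (Sections 5, 6 and 8). Sections 6 and 7 place the update and implementation after it, with no date. Protocol v3.0, dated 25 January 2024, describes the update and the DHPC in the past tense. That is 321 days, or 321/30.44 = 10.5 months, after the decision. The materials existed by then, but this does not date their national distribution. National reimbursement in Spain came on 1 May 2023 (Section 8.9), 52 days after the decision.

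**The plan's own figures.** None depends on these dates. As a yardstick, Section 8.5 gives a standard error of 1.7% and a 95% CI of 6.6% to 13.4% for 10% in 300 patients. Check: sqrt(0.10 × 0.90 / 300) = 0.0173, and 0.10 ± 1.96 × 0.0173 = 0.066 to 0.134. This reproduces.

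**Share of starts before distribution.** Assume a lag of L months (not in the documents) and even accrual over T months. The share is w = L/T.

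| Assumed lag | T = 48 (final) | T = 24 (interim) |
|---|---|---|
| 1 month | 1/48 = 2.1% | 1/24 = 4.2% |
| 3 months | 3/48 = 6.3% | 3/24 = 12.5% |
| 6 months | 6/48 = 12.5% | 6/24 = 25.0% |
| 9 months | 9/48 = 18.8% | 9/24 = 37.5% |

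If a registry reached its ceiling of 500 before 48 months at an even pace, T would be shorter and the share larger.

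**Slow early uptake.** Section 8.9 counts 54 pre-decision patients in ICC and 44 in SWIBREG. From 12 November 2021 to 10 March 2023 is 483 days, or 15.9 months, giving 54/15.9 = 3.4 and 44/15.9 = 2.8 per month. If that pace held during the lag and the registry later reached 500:

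- 1 month: 3.4/500 = 0.7% (ICC) and 2.8/500 = 0.6% (SWIBREG).
- 9 months: 30.6/500 = 6.1% (ICC) and 25.0/500 = 5.0% (SWIBREG).

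If the pace never rose, the even-accrual shares hold, but 48 months would yield only about 3.4 × 48 = 163 and 2.8 × 48 = 134 patients.

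**Effect on a pooled percentage.** Observed non-adherence = w × p_before + (1 − w) × p_after, so the excess over p_after is w × (p_before − p_after). Purely for illustration, take 30% before and 10% after, a 20-point gap:

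- 48 months, lags of 1, 3, 6 and 9 months: excess of 0.4, 1.3, 2.5 and 3.8 points.
- 24 months, same lags: 0.8, 2.5, 5.0 and 7.5 points.
- Slow early uptake in ICC, 9 months: 0.061 × 20 = 1.2 points.

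Against the plan's standard error of 1.7 points, this runs from negligible to several standard errors. The unknown lag and the assumed gap drive the result.

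**Why index date alone cannot classify every measure.** Suppose distribution on 10 June 2023 and a start on 1 April 2023. The lipid test due around week 12 (Sections 8.3.2 and 8.7) falls about 24 June. The 22-week limit for induction in Table 5 falls on 2 September. Both decisions come after distribution although the index date comes before it.

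**The case against.** The strongest reply is that the gap may be trivial. No distribution date is given, so nothing shows a long lag. The pre-decision counts suggest few early starters, and reimbursement in Spain probably shortens the window there, though 19 ENEIDA patients already had exposure before the decision. All of this stands. It limits the size of the problem but does not remove the conflict between Section 8.1 and the eligibility rules.

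Three stronger readings are tempting, and the documents do not support them. First, a reader might infer that early prescribers were unexposed to risk minimization. Section 6 says an existing Guide was updated, and adherence is also judged against the SmPC, so only content changed after Article 20 is affected. Second, a reader might infer that early prescribing is scored as failure of the measures. The study is descriptive with no success threshold (Section 8.5), and adherent early prescribing would count in their favour. Third, a reader might infer that every adherence percentage is biased by a known amount. The abstract says the changes concerned warnings and precautions in particular. Contraindicated use, for example, is not shown to depend on the update.

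It is also fair to say that Section 8.7 leaves detailed analysis to a SAP not seen here, and that Section 6 says the approach follows an already endorsed study. A calendar split may therefore be planned elsewhere, and the date may be deliberate. But eligibility, index date and the wording of Section 8.1 are fixed in the protocol, and they disagree there.

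**Conclusion.** The point holds as an internal contradiction with a consequence for interpretation. The cohort is described as post-implementation but selected from the decision date, and the protocol itself puts the updated materials after that date. Some starts that could not reflect the updated content are therefore pooled with starts that could.

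The size cannot be determined from the protocol. About 2-19% of the final cohort and 4-38% of the interim cohort would be affected, assuming even accrual and a lag of 1 to 9 months. The share would be roughly 0.6-6% of a full 500 if early accrual stayed at the pre-decision pace in ICC and SWIBREG. The effect on any percentage also depends on how far adherence differs before and after distribution, which is unknown. The concern is confined to measures that rest on content updated after Article 20, chiefly decisions at initiation. It should be corrected because the correction is cheap and bears directly on the study's stated question. It does not invalidate the design.

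**What to change.** 1. Reconcile Section 8.1 with Sections 8.2.2 and 8.2.4 so that the population is described by the date that selects it.
2. Record, for each country, the implementation dates of the updated HCP Guide, patient alert card and DHPC, and state which of them defines implementation.
3. Keep the 10 March 2023 eligibility date and all patients.
4. List the measures that depend on content updated after Article 20. For these, report adherence separately before and on or after the national implementation date. Classify initiation decisions by index date, and follow-up decisions (such as week-12 lipid testing, maintenance dose, or treatment changes after VTE) by the date of the decision or measurement.
5. Base the conclusion on the updated measures on the post-implementation results, and add the gap to Section 8.9.

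The cost is a small set of country dates and one additional classification variable. The documents do not say that the dates are on file, but the sponsor updated the materials and should be able to supply them. No patient is lost. The post-implementation estimates have a somewhat smaller n, and the pre-implementation group will probably be small, suitable for description only and not for a formal before/after comparison. If the lag proves short, the split will show that.
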